## **Scientific protocol**

### Human Subjects Involvement, Characteristics, and Design.

The study will enroll participating lay midwives from the department of Chimaltenango in central Guatemala. We anticipate enrolling 50 midwives in the project. There will be no restrictions in terms of age of the enrolled participants. Participants will be required to have basic Spanish language literacy in order to enroll. Some more elderly midwives will lack the required literacy and therefore will not be eligible to enroll. However, since the project involves use of a Spanish language interface on a cellular phone, this minimum requirement is essential to program success. Additionally, in our experience, most elderly, illiterate midwives in the communities where the project will be conducted are semiretired, and most practicing midwives are literate. Therefore, we do not anticipate that a significant portion of the eligible pool of midwives will be excluded from participation based on the literacy requirement. Recruitment identification will be by word of mouth through the local site partner's well-established contacts with midwives in the community.

In addition to enrollment of midwives, who will be the primary subjects of the project, the project will also collect demographic and health data on consenting pregnant patients of each practicing midwife, as well as neonates that are born to consenting pregnant patients during the project. No data will be collected on other patient populations other than these pregnant women and their neonates. Since this is a study of the use of mHealth technology to improve pregnancy and neonatal outcomes, it is important to collect data both on the pregnant women during the pregnancy, as well as data on the neonate in the first month of life.

Of the 50 recruited midwives, 25 will be randomly assigned to receive access to the mHealth technology immediately, whereas the remaining 25 will receive the technology after 6 months. Randomization of the midwives will be performed by entering their IDs into a list and running a simple program to generate an equal number of 1's and zeros, uniquely assigned to each midwife ID. For the second half of the 12 month implementation phase, all 50 midwives will have access to the technology. This randomized "stepped wedge" design is critical to the evaluation of the project, since baseline data (for example, on referral rates to local hospitals) is not readily available. Therefore, randomizing 50% of the enrolled midwives to a delayed intervention phase will allow us to collect high quality internal baseline data that can be used to make comparisons to the early intervention arm (e.g., to compare rates of referral). At the 6 month time-point, all midwives who did not initially receive the technology will do so, which will allow all participating midwives to benefit from the training and technology by the end of the project.

In the proposed work site, midwives attend on average 10-20 births per year. This means that, over 12 months of implementation, we will have the opportunity to collect process and outcomes data on a minimum of 500 pregnant women and neonates. We will restrict enrollment of pregnant women to those who are older than 18 years of age. This is the legal age of consent in Guatemala, and this is a necessary arrangement to ensure that only consenting adults are participating in the project, as opposed to minors who are pregnant. The average age of first pregnancy in the region is 22 years of age, so the number of pregnant women who are excluded from the project due to being legal minors will be minimal. Selection of patients will be on an ad hoc basis, based on the willingness and availability of patients.

Data collection will be coordinated by field staff from Wuqu' Kawoq, the collaborating local partner. In the early intervention arm, all data will be doubly entered onto paper forms and into the mHealth/EMR interface directly by collaborating midwives. In the later intervention arm, data will initially be entered only on paper forms by midwives and then, after receipt of the technology, will also be entered into the mHealth interface. Wuqu' Kawoq field staff will collect the paper forms and check them against the EMR for accuracy. After coding into the EMR, paper forms will be destroyed.

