## **Adequacy of Protection Against Risks**

### **Recruitment and Informed Consent**

Written or verbal informed consent will be obtained from all participating midwives and also from all pregnant patients of each participating midwife. There are two distinct settings and population for consenting study participants. The first group of participants is the midwives, who will be recruited and consented by the study coordinator at Wuqu' Kawoq. Midwives in Wuqu' Kawoq's catchment area will be contact by phone by the study coordinator to assess interest in the project. If a midwife expresses interest in participating they will be invited to a preliminary training session. During this training session, project staff (and in particular the study coordinator) will describe the full details of the study to potential midwife participants, including the nature of the subject's involvement in the study, the possible risks and benefits of participation, and the individual capacity to withdraw from the study at any time without consequence. The midwives will have the opportunity to ask questions about the study, after which consent to proceed will be obtained. The study coordinator will receive training in human subjects protection (e.g., CITI or the NIH module) prior to interacting with and obtaining consent with midwives.

The second group of participants that requires consenting is the pregnant mothers. All pregnant patients of each recruited midwife will be eligible for participation. Participating midwives will be encouraged to mention the study to all of their patients and to relay any potential interest in participating to the study coordinator. When a midwife identifies a pregnant subject for potentially participation, a single study staff member (a trained nurse working under the supervision of the study coordinator) will discretely visit the patient (and the biological father, if appropriate), at a location of their choosing (most likely to be the domicile of the pregnant patient) and again describe the details of the study, the risks and benefits, and the capacity to withdraw at any time without consequence, at which point verbal consent will be obtained for collection of data both during the pregnancy and in the neonatal period.

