**Additional Protections for Pregnant Women, Fetuses and Neonates.** This research involves the collection of demographic and health outcomes data on pregnant women and neonates. Importantly, the interventional component of the study involves an mHealth/EMR integration step and does not introduce novel or experimental technologies. All technologies that will be used in the mHealth arm are standard-of-care technologies (Doppler, blood pressure monitoring, pulse oximetry). Half of the enrolled participants will initially not receive any intervention. However, they will receive the current standard of care by lay midwives, with no interference in this usual process. Furthermore, for pregnant women and neonates who access the technology (either in the early access or later access arms), the expected result of the technology will be earlier and more timely referral to a higher level of medical care. At no point will the technology discourage accessing a higher level of care. Since the project holds out the potential for direct benefit to the pregnant woman and/or her fetus, consent will be obtained directly from the pregnant women to participate as outlined in 45cfr46 subpart B. The proposal does not include any inducements to early termination of a pregnancy, and it does not explicitly involve research on neonates of uncertain or non-viability, although in accordance with the proposal's plan to increase early access to medical care for all neonates, rates of neonatal mortality will be tracked.

**Additional Protections for Children.** This study involves collection of neonatal mortality rates and rates of early evaluation of neonates by a postnatal health care delivery team. As such, no direct interventions on children will be performed, and the study involves minimal risk to children. As outlined above, consent will be obtained from both biological parents at the time of enrollment of the pregnant patient in the study to permit collection of this data.

The study will not enroll pregnant patients prior to the legal age of informed consent in Guatemala (18 years).

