**Study**

**Title:** **Mobile Health Intervention to Improve Perinatal Continuum of Care**

**Total Planned Enrollment:** **1050**

TARGETED/PLANNED ENROLLMENT: Number of Subjects			
Ethnic Category	Sex/Gender		
	Females	Males(*)	Total
Hispanic or Latino	800	250	1050
Not Hispanic or Latino	0	0	0
Ethnic Category: Total of All Subjects *	800	250	1050
Racial Categories			
American Indian/Alaska Native	800	250	1050
Asian	0	0	0
Native Hawaiian or Other Pacific Islander	0	0	0
Black or African American	0	0	0
White	0	0	0
Racial Categories: Total of All Subjects *	800	250	1050

\* The “Ethnic Category: Total of All Subjects” must be equal to the “Racial Categories: Total of All Subjects.” \*\* Any children born in the study are considered part of the enrollment. With 500 anticipated births, 50% of these are anticipated to be male

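### Is the stated minimum of 500 women and neonates overstated because it allows for no refusals?

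*Protocol*

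**What the plan says.** The section on Human Subjects Involvement, Characteristics, and Design gives the number of midwives ("We anticipate enrolling 50 midwives in the project") and their workload ("In the proposed work site, midwives attend on average 10-20 births per year"). From these it concludes that over 12 months "we will have the opportunity to collect process and outcomes data on a minimum of 500 pregnant women and neonates". The same paragraph then limits enrolment to adult women, expects few to be lost that way, and adds: "Selection of patients will be on an ad hoc basis, based on the willingness and availability of patients".

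Other sections describe how a woman comes to be enrolled. Under Recruitment and Informed Consent, "Participating midwives will be encouraged to mention the study to all of their patients and to relay any potential interest", after which a nurse visits to obtain consent; the father takes part in that visit where appropriate. The paragraph on additional protections for children says that "consent will be obtained from both biological parents at the time of enrollment of the pregnant patient in the study".

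The Targeted/Planned Enrollment Table gives a total of 1,050 (800 female, 250 male), counts newborns as enrolled, and notes: "With 500 anticipated births, 50% of these are anticipated to be male". On timing, the design section says: "For the second half of the 12 month implementation phase, all 50 midwives will have access to the technology".

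**The concern.** A minimum reads as a number the study can count on. Here it equals all births attended at the lowest workload in the stated range, so a single refusal at that workload would put enrolment below it. The protocol gives several reasons to expect losses: the age limit, ad hoc selection, reliance on the midwife to pass on interest, the nurse's visit, and parental consent. No uptake rate is stated for any of them.

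The enrolment table uses the same 500 as the number of births planned for enrolment, so a count of births available seems to have become a count of participants. It can also look as though the floor in one section is the total in another.

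Apart from the 1,050 built on it, 500 is the only figure for women and neonates in the protocol. If readers or ethics boards took it as assured, they could expect a larger dataset than the study will deliver. They might also overlook that only about half of these births fall in the six months when the two randomised arms differ in access to the technology.

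**Working it through.** **Inputs.** Midwives: 50. Births per midwife-year: 10 to 20. Period: 12 months. All three come from the design section. Uptake: not stated, so 60%, 80% and 100% are shown as assumptions. One neonate per birth is also assumed.

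**Reproducing the plan's figures.**

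- Attended births = midwives × births per midwife-year × years. At the low end, 50 × 10 × 1 = 500, which matches exactly. The midpoint gives 50 × 15 = 750 and the high end 50 × 20 = 1,000.
- Table total = midwives + women + neonates = 50 + 500 + 500 = 1,050.
- Females = 50 + 500 + 250 = 800; males = 250.

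Every printed number is arithmetically correct. The total of 1,050 does use 500 women and 500 neonates with no reduction.

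**Uptake needed and women enrolled.** Uptake needed for 500 = 500 / attended births. Women enrolled = attended births × uptake.

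| Births per midwife-year | Attended births | Uptake needed for 500 | Enrolled at 60% | at 80% | at 100% |
|---|---|---|---|---|---|
| 10 | 500 | 100% | 300 | 400 | 500 |
| 15 | 750 | 67% | 450 | 600 | 750 |
| 20 | 1,000 | 50% | 600 | 800 | 1,000 |

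Turned round, the workload needed for 500 women is 500 / (50 × uptake): 12.5 births per midwife-year at 80% and 16.7 at 60%. Both lie inside the stated range.

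**Effect on the planned total.** At 10 births and 80% uptake, subjects = 50 + 400 + 400 = 850. At 60%, 50 + 300 + 300 = 650. At 15 births and 80%, 50 + 600 + 600 = 1,250. The planned 1,050 lies within this spread.

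**Months 1 to 6.** If births are spread evenly, half of 500 to 1,000 is 250 to 500 attended births, or 125 to 250 per arm, before refusals. This follows directly from the stated crossover at six months.

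**What the sentence claims.** It speaks of an opportunity to collect data. Read that way, 500 is a correct lower bound on births available, given 50 midwives and at least 10 births each on average. It is not a lower bound on women enrolled with data, and the sentence does not say that it is.

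**The case for a change.** The strongest case for a change rests on the enrolment table. The word opportunity may rescue the sentence in the design section, but the table concerns enrolment and explicitly counts newborns as enrolled. Its cells come out only if 500 women and 500 neonates are actually enrolled, so the number of births available is reused without discount. The protocol also gives its own reasons to expect losses. It calls exclusion of minors minimal, which is not zero, and under Potential Risks to Participants it says that some women may hide the pregnancy from everyone except the midwife. That makes a nurse's visit and the father's consent likely points of loss. Correcting the wording would cost almost nothing.

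Part of this stands. The protocol states no uptake rate, and 500 should not be read as a floor on enrolment.

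The rest does not carry.

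- The table is a plan and calls its births anticipated. A plan set at the bottom of a range of 500 to 1,000 already leaves room for loss: at the midpoint workload a third of births could go unenrolled and 500 would still be reached.
- Nothing makes 1,050 a ceiling, so a floor on availability and a target of the same size do not contradict each other.
- The 100% requirement is firm only for attended births. All pregnant patients of a midwife are eligible and data are collected during pregnancy, so a woman still pregnant at month 12 can contribute pregnancy data without a birth in the window.
- The limits on enrolment stand in the same paragraph as the 500, and the six-month crossover is stated openly. Which periods enter which comparison is commonly left to the statistical analysis plan.

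**Conclusion.** No change to the plan follows. The observation is accurate: 500 is the number of births attended at the low end of the workload, and the enrolment table uses it without a stated uptake. At that workload, assumed uptake of 80% or 60% would bring 400 or 300 women, a shortfall of 100 or 200. At 15 births per midwife-year, 500 is met with 67% uptake, and at 20 with 50%. The figure is therefore attainable within the protocol's own range, and neither it nor the 1,050 is shown to be wrong.

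The protocol ties no power calculation, comparison or stopping or decision rule to either number. Rewording would keep both, leave recruitment and design as they are, and still lack the one absent item, an uptake rate, which the protocol gives no basis for estimating. Analysts will work with the women actually enrolled and can report births attended beside them.

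This conclusion assumes that 50 midwives enrol, that their average workload lies between 10 and 20 births a year, and that 1,050 is a target and not a cap. It would need another look if a precision or power claim were later built on 500 enrolled women.

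### No single binding rule fixes which women the midwives bring to consent, so enrolled case mix could differ by arm

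*Protocol*

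**What the plan says.** All references are to the Protocol; the SAP is not at hand.

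- **Allocation** (Human Subjects Involvement, Characteristics, and Design): of 50 midwives, "25 will be randomly assigned to receive access to the mHealth technology immediately" and the other 25 receive it after 6 months. The example given for the between-arm comparison is referral ("e.g., to compare rates of referral").
- **Selection of women** (same section): "Selection of patients will be on an ad hoc basis, based on the willingness and availability of patients". Midwives attend 10-20 births a year, and the section expects the chance to collect data on "a minimum of 500 pregnant women and neonates".
- **Route to consent** (Recruitment and Informed Consent): "All pregnant patients of each recruited midwife will be eligible for participation". The section opens by speaking of consent from all of them. Then: "Participating midwives will be encouraged to mention the study to all of their patients and to relay any potential interest". The nurse's consent visit follows "When a midwife identifies a pregnant subject for potentially participation". No other route to a woman is described.
- **Knowledge of arm**: "In the later intervention arm, data will initially be entered only on paper forms by midwives", while early-arm midwives also use the mHealth interface. Potential Risks to Participants names possible resentment among late-arm midwives, with orientation and reassurance as mitigation. The protocol does not use the word unblinded; it follows from the design.

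**The concern.** In a cluster-randomised design, randomising the midwives protects the comparison of midwives. It does not by itself protect the comparison of the women who enter the dataset if someone who knows the allocation influences which women those are. Here that person is the midwife. Nothing in the protocol provides for enrolling women before allocation, so enrolment after it is the likely reading, although this is not stated.

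If one arm brings forward a larger share of higher-risk women, its referral rate rises with no effect of the technology; if it brings forward more lower-risk women, the rate falls. Imbalance in the recorded characteristics of enrolled women could be partly seen and adjusted for. Women never mentioned or relayed leave no record, and no later analysis can recover them. For that reason the approach rule belongs in the protocol.

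**Working it through.** **1. The plan's own figure.** 50 midwives x 10 births = 500, which reproduces the stated minimum; 50 x 20 = 1000. The share of attended births needed to reach 500 is:
- 10 births per midwife: 500/500 = 100%
- 15 births: 500/750 = 67%
- 20 births: 500/1000 = 50%

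The figure therefore fits a consecutive offer at the low end of the range and partial enrolment at the high end. It does not settle which reading is meant.

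**2. Women available while the arms differ (months 1-6).** Per arm, with births spread evenly: 25 x 10 x 0.5 = 125 to 25 x 20 x 0.5 = 250.

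**3. Illustration of a spurious shift.** Every input is assumed; none is in the protocol. Suppose 20% of patients are high-risk with 40% referred, the other 80% have 5% referred, and the technology has no effect. With eh and el the enrolled shares of high- and low-risk women,

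referral among enrolled = (0.2 x eh x 0.40 + 0.8 x el x 0.05) / (0.2 x eh + 0.8 x el).

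When eh = el, this is 12.0%. Let the delayed arm enrol the base share of everyone, and let the early arm enrol more of one risk group only:

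| Base share | Early arm enrols | Referral, early arm | Shift (points) | Risk ratio |
|---|---|---|---|---|
| 60% | 90% of high-risk | 0.096/0.66 = 14.5% | +2.5 | 1.21 |
| 60% | 90% of low-risk | 0.084/0.84 = 10.0% | -2.0 | 0.83 |
| 80% | 100% of high-risk | 0.112/0.84 = 13.3% | +1.3 | 1.11 |
| 80% | 100% of low-risk | 0.104/0.96 = 10.8% | -1.2 | 0.90 |
| 100% | everyone, both arms | 12.0% | 0 | 1.00 |

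**4. Against sampling error.** At 60% enrolment there are 75 to 150 women per arm. The standard error is sqrt(2 x 0.12 x 0.88 / n): 5.3 points at n = 75 and 3.8 at n = 150. With 3 or 6 women per midwife and an assumed intracluster correlation of 0.05, the design effect is 1.10 or 1.25, giving 5.6 or 4.2 points. At 80% enrolment (100 to 200 women) the unclustered standard error is 4.6 to 3.2 points. Every shift in the table is below one standard error.

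**5. Sensitivity to the assumed inputs.** With a high-risk share of 10-30%, referral of 50% v 5% or 40% v 10%, and 75-90% v 60% enrolment of high-risk women, the shift is 0.7 to 4.1 points. The largest case has an 18.5% base rate and a standard error of sqrt(2 x 0.185 x 0.815 / n) = 6.3 points at n = 75 and 4.5 at n = 150, so it too is below one standard error.

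**6. Would a count of eligible and enrolled women show it?** The ratios below are the enrolment gap divided by its standard error, with 125 to 250 births per arm (5 to 10 per midwife).
- Largest downward case in the table (early arm enrols 0.2 x 0.6 + 0.8 x 0.9 = 84%, against 60%): 4.4-6.2 ignoring clustering, 4.0-5.2 at an assumed intracluster correlation of 0.05, 3.0-3.2 at 0.3.
- Largest upward case in the table (0.2 x 0.9 + 0.8 x 0.6 = 66%, against 60%): 1.0-1.4 ignoring clustering, 0.9-1.2 at 0.05, about 0.7 at 0.3.

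A count could reveal the first pattern if it is accurate, but hardly the second.

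**The case against.** The strongest reply is that there is no contradiction. The selection sentence is qualified by the patients' own willingness and availability, so the woman decides, and the consent section says whom to tell and what to relay. Tell everyone, enrol the willing is a coherent reading. This stands: a reader might infer that the two sections contradict each other, and they do not strictly do so.

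A reader might also infer that nothing addresses whom a midwife mentions. That goes too far, because the consent section encourages mention to all and relay of any interest. One nurse takes consent, all patients are eligible, midwives are trained to hold back discussion of the device's utility until after consent, and the coordinator's random visits look for deviations. What remains is narrower: mention is encouraged rather than required, and nothing described verifies which women were told or relayed. A midwife who mentions the study only to women who worry her would still be within the selection sentence and would fall short only of an encouragement.

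Two further inferences lack support. The protocol does not link late-arm resentment to recruitment effort. The 500 minimum is evidence neither of planned partial sampling nor of an intended consecutive offer.

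Finally, materiality is not demonstrated, since every input to the illustration is assumed, and reporting of case mix by arm may sit in an SAP that is not shown. Both points hold. They cap the weight of the finding and make the wording the main fix.

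**Conclusion.** The point holds as an unreconciled wording tension with a real route to bias. As written, the plan permits arm-dependent enrolment, because the randomised midwives know their arm and stand between every woman and the consenting nurse. It does not show that such enrolment will happen, and neither size nor direction can be estimated from the document. On the main set of assumed inputs the spurious referral difference runs from about -2.0 to +2.5 points, and up to 4.1 points on the wider set, always below one standard error at the planned numbers. A small bias of this kind does not shrink with more women and would be read as an effect of the technology. This is an inexpensive improvement rather than a flaw that invalidates the comparison. Confidence is medium.

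**What to change.** **Main change.** Reconcile the design section and Recruitment and Informed Consent into one rule: every eligible adult pregnant patient of a participating midwife is offered the study consecutively, with the same script in both arms, and is relayed to the nurse only if she agrees. The last condition respects women who conceal a pregnancy, a risk the protocol itself names.

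**Secondary check.** Each midwife keeps an anonymous count of women eligible, offered and relayed, checked at the coordinator visits already planned. The design section's limit on collecting data from other patients should be worded to allow these counts. No outcome data on non-consenting women are needed.

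**Cost.** A wording amendment at both IRBs and a short count sheet. The counts are self-reported by unblinded midwives, and one who mentions fewer women may also count fewer. They would be clustered by midwife and would detect differential enrolment only partly.
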